6.4. Study Intervention Compliance

The prescribed dosage, timing and mode of administration of study medication may not be changed.

Study medication accountability and subject compliance will be documented throughout the treatment period using study-specific study medication dispensing and return record forms.

Participants will be asked to return all unused medication. From Visits 3 to 5 (weeks 4 to 16), the study medication dispensed at the previous visit will be retrieved by the Investigator and compliance assessed by tablet count.

Non-compliance is defined as taking less than 80% of study medication during any visit-to-visit evaluation period.

Participants exhibiting non-compliance will be reminded about the importance of being compliant with the study dosing regimen.

6.5. Concomitant Therapy

Any medication or vaccine (including over-the-counter or prescription medicines, vitamins, and/or herbal supplements) that the participant is receiving at the time of enrollment or receives during the study will be recorded along with:

- Reason for use.
- Dates of administration including start and end dates.
- Dosage information including dose and frequency.

In particular, all pain medication taken on a PRN basis (e.g. paracetamol, up to a maximum of 4,000mg/day; NSAIDs) will be recorded in the dedicated section of eCRF.

In addition, patients will continue to use their regular non PRN pain medication, if taken, (e.g. oxycodone, codeine, botulinum toxin, gabapentin, nortriptyline, muscle relaxants, analgesics) which should remain stable from the 4 weeks prior to randomization visit and at least for the first 4 weeks of the study.

If the patient is using a combination analgesic that contains paracetamol, extreme caution must be exercised in the use of PRN medications containing paracetamol, so as not to exceed a paracetamol total daily dose of 4000 mg (see section 6.5.2)

Medical Monitor should be contacted if there are any questions regarding concomitant or prior therapy.

6.5.1. Rescue Medicine

Not Applicable

6.5.2. Excluded Medicine

Treatment with the following drugs is not allowed 4 weeks before randomization, throughout the study and up 2 weeks after the last dose of study drug:

- Monoamine oxidase inhibitors (MAOIs),
- Levodopa infusion,
- Pethidine,
- Fluvoxamine,
- Fluoxetine,
- Combination analgesic products including paracetamol are permitted, but extreme caution must be exercised in the use of PRN medications containing paracetamol so as not to exceed a total daily dose of 4000mg paracetamol

The use of any prohibited concomitant medication is a protocol deviation and should be recorded.

6.5.3. Permitted Medication

Selective serotonin reuptake inhibitors (SSRIs) ,other than fluoxetine or fluvoxamine, selective serotonin-norepinephrine reuptake inhibitors (SNRIs), tricyclic and tetracyclic antidepressants can be administered provided they remain at the lowest effective dose and remain stable throughout the study

Dextromethorphan, sympathomimetics, nasal and oral decongestants or cold medicinal products containing ephedrine, pseudoephedrine, phenylephrine or phenylpropanolamine are permitted if used for treating cough but must be used with caution.

6.6. Dose Modification

Not applicable.

6.7. Intervention after the End of the Study

Phone call at one week after EoT.

7. Discontinuation of Study Intervention and Participant Discontinuation/Withdrawal

7.1. Discontinuation of Study Intervention

Not applicable

7.2. Participant Discontinuation/Withdrawal from the Study

- A participant may withdraw from the study at any time at his/her own request, or may be withdrawn at any time at the discretion of the investigator for safety, behavioral, compliance, or administrative reasons.
- If the participant withdraws consent for disclosure of future information, the sponsor may retain and continue to use any data collected before such a withdrawal of consent.
- If a participant withdraws from the study, he/she may request destruction of any samples taken and not tested, and the investigator must document this in the site study records.
- See SoA for data to be collected at the time of study discontinuation and follow-up and for any further evaluations that need to be completed.
- Pregnant participants must be withdrawn from the study without delay

Participants who are withdrawn from the study will not be replaced.

In the event that a subject discontinues from the study prematurely due to an AE or SAE, they will be followed until the event has resolved (returns to normal or baseline values) or has stabilised.

The reason for withdrawal of a subject from the study must be fully documented in the eCRF as well in source documents.

Any major or critical deviation which may have an impact on study results and or safety of the participants should be immediately reported to Sponsor/CRO and notified to Regulatory Authorities (EC/CA) according to local regulations. A decision will be taken by the Sponsor, after consultation with the medical monitor as to whether or not the subject affected by the departure from the protocol, is to continue in the study. A deviation log will be maintained to track actual deviations and decisions taken, including all deviations occurred.

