9.3. Populations for Analyses

For purposes of analysis, the following populations are defined:

| Population | Description |
|-------------------|---|
| Full analysis set | The FAS is defined as all randomized subjects in the study, with at least one measurement of the primary efficacy variable following at least one dose of study medication. Summaries on the FAS will be performed for all efficacy endpoints. Subjects in this |

| | |
|--------------|---|
| | analysis set will be summarized according to the treatment they were randomly assigned to. |
| Per Protocol | The PP Set will be a subset of subjects in the FAS who completed the study and for whom no relevant protocol deviations were documented. Identification of relevant protocol deviations will occur on a blinded review meeting preceding database lock. A second analysis of the primary efficacy endpoint will be based on the PP Set. All subjects in the PP Set will be summarized according to the treatment they were assigned to. |
| Safety | The Safety Set will include all randomized subjects assigned to study intervention and who take at least 1 dose of study medication. The Safety Set will be used for the analysis of all safety endpoints. All subjects in the Safety Set will be summarized according to the treatment they actually received (according to the Drug Accountability eCRF page). |

The decision whether a protocol deviation is relevant or not for the exclusion of participants from the per protocol (PP) set will be made case-by-case in a blind data review meeting.

The primary analysis of the primary efficacy variable will be based on the FAS data set. A secondary analysis of the primary efficacy parameter will be based on the PP set.

All other secondary efficacy analyses will be based on the FAS.

Safety analyses will be based on the safety analysis (SA) set.

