6.1. Disposition

A listing of randomisation information (including randomisation and kit number) for all randomised subjects will be produced.

Subject disposition will be summarised for the following categories: subjects in the All Enrolled, FAS, PP Set and Safety Set. A disposition of subjects includes the number and percentage of subjects who were enrolled, subjects that were screening failures, subjects randomised and subjects who completed the study, subjects who discontinued from the study, and subjects that were unblinded during the study. The number of subjects will be displayed by treatment group and overall, except screening failures where counts will only be displayed in the overall group. The reasons for study discontinuation may include any of

the following: Lost to Follow-up, Subject withdraws consent, Death, Adverse event, Physician decision, Pregnancy, Protocol violation, Study terminated by the Sponsor, and Other. The reasons for study discontinuation will also be summarised in this table. The percentages will be based on the number of subjects randomised.

Disposition data, displaying both randomised and actual treatment in case of randomised/treated subjects, will be listed, for all enrolled set.

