10.1. Primary Efficacy Endpoint

Pain severity data will be derived from the daily diary.

The primary endpoint evaluated in this study is the mean change in pain severity (“average worst pain experienced in the last 7 days”, i.e. average of the worst pain score on each of the 7 days preceding the site visit), as assessed by an 11-point NRS, from baseline to Week 16. For efficacy analysis, at least 4 out of 7 daily pain scores are needed to calculate a valid average over 7 days.

The null hypothesis for the primary endpoint is that safinamide is no better than placebo in managing pain; thus $\mu(\text{Safinamide}) > \mu(\text{Placebo})$, where μ represents the population mean change in pain severity score from baseline at Week 16 and a negative change would indicate improvement.

The primary efficacy endpoint, change from baseline to Week 16 in pain severity score, will be analysed using a mixed model repeated measures (MMRM) using visit on subject ID as

the repeated factor with unstructured covariance term (REPEATED VISIT/SUBJECT=SUBJID TYPE=UN). If convergence is not achieved, then other covariance structures will be investigated such as compound symmetric (TYPE=CS). The model will include fixed effects terms for treatment, country, visit and regular pain medication use at baseline (yes or no) and covariate term for pain severity score at baseline. The method above (e.g. MMRM) is unbiased under the MAR assumption and can be thought of as aiming to estimate the treatment effect assuming that after withdrawal, subjects would have continued on a similar trajectory to their peers in the same arm who have the same covariates.

The likelihood-based mixed-effect model repeated measure will be performed using a SAS PROC MIXED procedure, and the Kenward-Roger method for degrees of freedom will be applied. The restricted maximum likelihood (REML) method will be used for estimation. The least square (LS) means of change from baseline in pain severity along with the associated SE and 95% CIs will be calculated from the model at each time point. The LS mean difference between the treatment groups at Week 16 will also be reported, along with the corresponding SE, 95% CIs, and the p-value derived for the difference between treatment arms (safinamide – placebo). No adjustment is being made for multiple comparisons.

Results for time points other than Week 16 (Weeks 4 and 8) will be presented in both the above discussed model-adjusted and descriptive forms.

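### Section 7.2 permits withdrawal from the study for poor compliance or a protocol deviation, so the Week 16 pain score of such patients would not be collected and the primary estimate could drift toward the effect in adherent patients

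*Protocol*

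**What the plan says.** **Withdrawal.** Protocol 7.2 deals with leaving the study, not only with stopping drug. A participant "may be withdrawn at any time at the discretion of the investigator for safety, behavioral, compliance, or administrative reasons". For major or critical deviations the sponsor decides, after consulting the medical monitor, "whether or not the subject affected by the departure from the protocol, is to continue in the study". It adds: "Participants who are withdrawn from the study will not be replaced".

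**Stopping drug but staying in.** The whole text of Protocol 7.1, Discontinuation of Study Intervention, is "Not applicable". Under Visit 5 in Protocol section 8, premature discontinuation leads to the end-of-treatment assessments, and no later pain score is scheduled.

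**Non-compliance.** Protocol 6.4 defines it as taking under 80% of study medication in any interval between visits and prescribes only this: "Participants exhibiting non-compliance will be reminded about the importance of being compliant with the study dosing regimen".

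**Deviations in the analysis.** Protocol 9.3 and SAP 4.3 handle them through the Per Protocol Set: "Identification of relevant protocol deviations will occur on a blinded review meeting preceding database lock". The reasons for study discontinuation that SAP 6.1 says may occur include "Physician decision, Pregnancy, Protocol violation, Study terminated by the Sponsor, and Other".

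**Primary analysis.** SAP 10.1 fits an MMRM on the FAS by randomised arm. It describes its target as the effect "assuming that after withdrawal, subjects would have continued on a similar trajectory to their peers in the same arm" who share the same covariates. Compliance is not among the model terms.

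**The concern.** The FAS analysis is meant to compare patients as randomised. Poor compliance and deviations can be linked to poor tolerability or lack of benefit. If patients leave the study for those reasons, their Week 16 values are missing for a reason that may relate to the outcome, and the patients left in the arm are more adherent than the arm as randomised. The FAS result would then lean toward the effect in adherent patients without being labelled as such.

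The loss looks avoidable. Protocol 6.4 already has a milder response to non-compliance, and the Per Protocol Set already has a blinded route for deviations. SAP 11.1.5 and 11.1.6 tabulate adverse events leading to treatment discontinuation separately from those leading to study discontinuation, so the analysis plan already treats these as different events.

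**Working it through.** **1. The plan's own figures.** For a 1-point difference, SD 1.5, 2:1 allocation, 5% significance (two-sided assumed, since the sample-size text does not say) and 80% power, a noncentral-t calculation gives 28 + 56 = 84 completers, with power 81.2%. With 20% dropout, 84/0.80 = 105 randomised. Both match Protocol 9.2. The plan therefore expects 105 - 84 = 21 patients without completion, and it does not split them by reason. The active arm has 105 x 2/3 = 70 patients.

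**2. What happens to a withdrawn patient's data.**
- Scores before withdrawal are kept. One post-dose score is enough to stay in the FAS (Protocol 9.3, SAP 4.3).
- Tablet counts start at Visit 3 (Protocol 6.4), when the Week 4 pain score is also due. A patient withdrawn on a tablet count would normally have at least that score.
- An early-termination diary score is planned (Protocol 8.1.1). SAP section 4 summarises data by eCRF visit name, so this score could be filed under Visit 5. The documents do not settle the point. Either way it is not a Week 16 score.

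**3. Size of the drift.** Assumptions, none given in the documents:
- a share w = 5% or 10% of active patients (3.5 to 7 of 70) is withdrawn;
- they have zero effect at every visit, and stayers have 1 point at every visit;
- placebo withdrawals cause no bias;
- variances are equal across visits, with common correlation r = 0.5 to 0.7;
- the model has visit-specific means.

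The as-randomised effect is (1 - w) x 1.0, that is 0.95 or 0.90.

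The withdrawn patients' earlier scores are on average 1 point worse than the stayers'. The model carries forward b of that point to Week 16, where b is the sum of the regression slopes of Week 16 on the observed visits. The overstatement is w x (1 - b).

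- Earlier scores uninformative: b = 0.
- Week 4 only: b = r.
- Weeks 4 and 8: b = 2r/(1 + r), which is 0.667 at r = 0.5 and 0.824 at r = 0.7.

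| Scores available | w = 5% | w = 10% |
|---|---|---|
| None informative | 0.05 | 0.10 |
| Week 4, r = 0.5 | 0.05 x 0.5 = 0.025 | 0.10 x 0.5 = 0.050 |
| Week 4, r = 0.7 | 0.05 x 0.3 = 0.015 | 0.10 x 0.3 = 0.030 |
| Weeks 4 and 8, r = 0.5 | 0.05 x 0.333 = 0.017 | 0.10 x 0.333 = 0.033 |
| Weeks 4 and 8, r = 0.7 | 0.05 x 0.176 = 0.009 | 0.10 x 0.176 = 0.018 |

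With earlier scores in the model, the overstatement is about 0.01 to 0.05 points. If the withdrawn patients kept half the benefit, every entry halves. The model terms listed in SAP 10.1 include no treatment-by-visit term. Fitted as listed, the model would let Week 4 and 8 scores enter the treatment estimate directly, and the table would be only a guide.

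**4. Power.** Keeping about 6 or 10 of these patients gives 60/30 or 63/31 completers. At an unchanged 1-point effect, power is 83.9% or 85.2%. At the diluted effects from step 3 it is 80.0% (0.95, 60/30) or 77.2% (0.90, 63/31), against 81.2% now. Under these assumptions there is no power gain.

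**The case against.** The strongest reply is that 7.2 grants a discretion and nothing in the documents predicts its use. The specific rule for non-compliance is a reminder, and the SAP 6.1 list is a set of disposition categories, not evidence of removals. This stands: the number of patients affected is unknown and could be zero.

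A reader might infer that such withdrawal repeats the Per Protocol exclusion inside the FAS. The documents do not support that. The Per Protocol Set drops the patient altogether, whereas a withdrawn patient with one post-dose score stays in the FAS, in the randomised arm, with all observed scores used.

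A reader might also infer that the MMRM simply gives these patients the course of compliant peers, so that the full 0.05-0.10 points is the expected bias. That ignores the patient's own Week 4 and 8 scores, which the unstructured covariance uses. The SAP speaks of same-arm peers, not compliant ones; that those who stay are mostly adherent is an inference. Zero benefit is also an extreme assumption, because a patient taking 75% of tablets in one interval already counts as non-compliant.

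Finally, SAP 10.2(b) tests the same-arm assumption by imputing each discontinued patient's worst own score, in the FAS. That is a useful partial check. But it covers all discontinuations together, leaves the primary estimate as it is, and recovers no data.

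**Conclusion.** The point holds in a limited form. The current text allows patients who could still be assessed to be taken out of the study for compliance or for a deviation, and their true Week 16 pain score is then not collected. The primary estimate can drift toward the effect in adherent patients.

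The likely size is small: roughly 0.01-0.05 on a 1-point effect, resting on the assumed 5-10% of active patients, no benefit in them, and correlation 0.5-0.7. The 0.05-0.10 range is an upper bound for uninformative earlier scores. The sample size is not in error on this account, and more completers should not be presented as more power. The case for acting is that the change is cheap and that uncollected scores cannot be recovered at analysis.

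**What to change.** **Protocol 7.2.** State that non-compliance, or a protocol deviation that raises no safety concern, is not by itself a reason to end study assessments. State that participants who still consent continue the diary and visit assessments already scheduled at Weeks 4, 8 and 16. Such deviations are then dealt with through the Per Protocol Set at the blinded review in 9.3.

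**Left unchanged.** Withdrawal for safety, behavioural or administrative reasons and for pregnancy, the participant's own right to withdraw, and every decision about study drug.

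**SAP 6.1.** Align the list of reasons for study discontinuation with the revised 7.2.

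**Cost.** A short passage in a protocol amendment and one SAP line, with no new visits or instruments. It helps only patients still under follow-up when it takes effect. The FAS estimate may be slightly less favourable because poor compliers stay under observation.

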7.3. Lost to Follow Up

A participant will be considered lost to follow-up if he or she repeatedly fails to return for scheduled visits and is unable to be contacted by the study site.

The following actions must be taken if a participant fails to return to the clinic for a required study visit:

- The site must attempt to contact the participant and reschedule the missed visit as soon as possible and counsel the participant on the importance of maintaining the assigned visit schedule and ascertain whether or not the participant wishes to and/or should continue in the study.

- Before a participant is deemed lost to follow up, the investigator or designee must make every effort to regain contact with the participant (where possible, 3 telephone calls and, if necessary, a certified letter to the participant's last known mailing address or local equivalent methods). These contact attempts should be documented in the participant's medical record.

8. Study Assessments and Procedures

- Study procedures and their timing are summarized in the SoA. Protocol waivers or exemptions are not allowed.
- Immediate safety concerns should be discussed with the sponsor immediately upon occurrence or awareness to determine if the participant should continue or discontinue study intervention.
- Adherence to the study design requirements, including those specified in the SoA, is essential and required for study conduct.
- All screening evaluations must be completed and reviewed to confirm that potential participants meet all eligibility criteria. The investigator will maintain a screening log to record details of all participants screened and to confirm eligibility or record reasons for screening failure, as applicable.
- Procedures conducted as part of the participant's routine clinical management and obtained before signing of the ICF may be utilized for screening or baseline purposes provided the procedures met the protocol-specified criteria and were performed within the time frame defined in the SoA.
- The maximum amount of blood collected from each participant over the duration of the study, including any extra assessments that may be required, will not exceed 20 mL. Repeat or unscheduled samples may be taken for safety reasons or for technical issues with the samples.
- Local labs will be used in this study

Visit 1: Screening visit (7 to 14 days before Day1)

The screening visit (Visit 1) should take place at least 7 days prior to Visit 2 to allow sufficient time to receive lab results and for subject to complete 7 days' worth of diary data, to fully assess eligibility.

- Obtain written informed consent.
- Record details in IWRS (Section 6.3) for screening number allocation.
- Record demographic data, including age, sex, ethnicity, smoking and alcohol use.
- Record of medical history and PD diagnosis, including Hoehn and Yahr stage.
- Recording of prior medications, concomitant medications (including PRN medication for pain) and therapies (Section 6.5).
- Neurological examination.
- MMSE (Section 8.2.3).
- Physical examination (Section 8.2.1).
- Vital signs (heart rate, systolic and diastolic blood pressure) measured after at least 5 minutes in the supine position (Section 8.2.2).
- Blood sampling for clinical laboratory assessments (haematology and clinical chemistry, including liver function tests) (Section 8.2.4 & 10.2).
- Show the subject how to use the electronic diary (Section 8.1.1).
- Check of inclusion and exclusion criteria (Sections 5.1 and 5.2).

- Issue electronic diary with instructions for the NRS pain assessment and PRN pain medication intake to be completed daily over the seven consecutive days immediately prior to the baseline visit (Visit 2).
- When agreeing the visit schedule with the subject, bear in mind that scales & questionnaires should be done at approximately the same time of day, preferably at least one hour after the usual morning L-Dopa dose (and study medication), when participant is in an optimal ON state.

Visit 2: Baseline visit (Day 1)

At Visit 2, if subject is eligible, the baseline values will be established, and the first dose of study medication will be administered under supervision at the site.

- NRS score of pain intensity > 4 for eligibility, as recorded in the electronic diary. (Section 8.1.1).
- Check of inclusion and exclusion criteria. If participant is eligible, upon completing the data entry in the EDC system the randomization form will appear to randomise subject.
- Vital signs (heart rate, systolic and diastolic blood pressure) measured after at least 5 minutes in the supine position.
- Urine sampling for urine (dipstick) pregnancy test for women of child-bearing potential (WOCB).
- Completion of MDS-UPDRS (part IB and II) and HADS by the subject (Section 8.1).
- Completion of MDS-UPDRS (part IA, III and IV) and CGI-S by the rater (Section 8.1).
- Administer subject's first dose of study medication (50 mg) at the study centre.
- Instruct participants to take the study medication, once daily, in the morning, along with their usual dose of L-Dopa. During Week 1 subject will take 50 mg, which will be increased up 100 mg at home on Day 8.
- Dispense study medication for the next 28 days.
- Re-issue electronic diary with instructions for the NRS pain assessment to be completed daily over the 7 consecutive days immediately prior to the visit at week 4 (Visit 3) and the intake of PRN pain medication to be recorded daily according to use.
- Recording of prior medications, of concomitant medications and therapies.
- Recording of AEs (Section 8.3).

When scheduling Visits 3, 4 and 5, bear in mind that:

- where possible, the subject should be in an optimal ON state, i.e. at least 1 hour after the morning dose L-Dopa and study medication.
- the questionnaires should be completed at the approximately on the same time of the day as at the baseline visit.

COVID- 19 outbreak: in order to ensure the continuity of the study, limiting the subjects' exposure to infection and overcoming travel restriction imposed by governments, a Contingency

Plan has been finalized describing alternative procedures to be adopted in the study in order to mitigate the restrictions and keeping participants in the trial (see Appendix 10 for details).

Visit 3 & Visit 4: interim visits (Day 28 & Day 56)

- Completion of MDS-UPDRS (part IB and II), and PGI-C by the subject.
- Completion of MDS-UPDRS (part IA, III and IV), CGI-S and CGI-C by the rater.
- Recording of concomitant medications and therapies.
- Recording of AEs.
- Drug accountability.
- Review and evaluate daily diary (provide additional daily diary training, as required).
- Re-issue electronic diary at weeks 4 and 8, with instructions for the NRS pain assessment and the intake of PRN pain medication to be completed daily over the 7 consecutive days immediately prior to the next visit (Visits 4 & 5).
- Dispense study medication for next period.

COVID- 19 outbreak: in order to ensure the continuity of the study, limiting the subjects' exposure to infection and overcoming travel restriction imposed by governments, a Contingency Plan has been finalized describing alternative procedures to be adopted in the study in order to mitigate the restrictions and keeping participants in the trial (see Appendix 10 for details).

Visit 5: End of Treatment (Day 112)

Following completion of 16 weeks' of treatment or in the event of premature discontinuation, the following End of Treatment (EOT) assessments and procedures should be performed.

- Neurological & Physical examination.
- Vital signs (heart rate, systolic and diastolic blood pressure measured after at least 5 minutes in the supine position).
- MDS-UPDRS (part IB and II), HADS and PGI-C completed by the participant.
- MDS-UPDRS (part IA, III and IV), CGI-S and CGI-C completed by the rater.
- Obtain blood sample for clinical laboratory assessments (haematology and clinical chemistry).
- Obtain urine sample only for WOCBP for urine (dipstick) pregnancy test.
- Record any changes or new concomitant medications and therapies.
- Record any AEs.
- Review and evaluate daily e-diary.
- Drug (all used & unused study medication) and final accountability.
- Collect e-diary.
- Agree on day & time for the follow up call in one weeks' time.

COVID- 19 outbreak: in order to ensure the continuity of the study, limiting the subjects' exposure to infection and overcoming travel restriction imposed by governments, a Contingency Plan has been finalized describing alternative procedures to be adopted in the study in order to mitigate the restriction and keeping participants in the trial (see Appendix 10 for details)

